2.1 Primary Objective

1. To determine the rate of complete cell cycle arrest, defined by Ki67 $\leq 2.7\%$, following 2 weeks (C1D15) of neoadjuvant PD 0332991 in combination with anastrozole in women with clinical stage II or III ER+/HER2- breast cancer without PIK3CA hot spot mutation (PIK3CA Wild Type Cohort).
2. To determine the rate of complete cell cycle arrest, defined by Ki67 $\leq 2.7\%$, following 2 weeks (C1D15) of neoadjuvant PD 0332991 in combination with anastrozole in women with clinical stage II or III ER+/HER2- endocrine-resistant breast cancer.

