12.0 MEASUREMENT OF EFFECT

12.1 Neoadjuvant Treatment

Complete cell cycle arrest: This is defined as $\text{Ki67} \leq 2.7\%$, which will be assessed at C1D1, C1D15, and surgery. In patients without C1D15 Ki67, Ki67 on D15 of subsequent cycles could be used instead.

Clinical Evaluation: Prior to Cycle 0 (or performed during pre-registration for study NCI 9170), and at the end of each neoadjuvant treatment cycle cycles (that is, at the end of Cycles 1-4) the longest axis and the perpendicular axis of the measurable lesion should be measured and recorded in metric notation by tape, ruler or caliper technique on the case report forms.

Radiologic evaluation of tumor size: Mammogram and ultrasound imaging will be performed prior to Cycle 0 (or performed during pre-registration for study NCI 9170) and at the end of Cycle 4 combination therapy for bidimensional measurement of the tumor.

WHO criteria will be used to assess clinical and radiologic responses.

Complete Response (CR) is defined as the disappearance of all known disease based on a comparison between the pre-treatment measurements and the measurements taken at the completion of neo-adjuvant therapy (that is, at the end of cycle 4 neo-adjuvant combination therapy). In addition there is no appearance of new lesions.

Partial Response (PR) is defined as a 50% or greater decrease in the product of the bi-dimensional measurements of the lesion (total tumor size) between the pre-treatment measurements and the measurements taken at the completion of neo-adjuvant therapy (that is, at the end of cycle 4 neo-adjuvant combination therapy). In addition there can be no appearance of new lesions or progression of any lesion.

No Change (NC): a 50% decrease in total tumor size cannot be established nor has a 25% increase in the size of the lesion been demonstrated.

Progressive Disease (PD): A 25% or greater increase in the total tumor size of the lesion from its pretreatment measurements or the appearance of new lesions.

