12.3 Surgery

A pathologic complete response (pCR) is defined as no histology evidence of invasive tumor cells in the surgical breast specimen and sentinel or axillary lymph nodes.

All eligible women who have been begun treatment with combination therapy and have tumor Ki67 determined on C1D15 (or a subsequent cycle) are included in the analysis of complete cell cycle arrest. Women with tumor Ki67>2.7% on therapy are considered to have a non-complete cell cycle arrest.

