15.2 Primary Endpoint

The primary endpoint of this trial is complete cell cycle arrest. All eligible women who begin combination treatment and have an evaluable tumor Ki67 on Cycle 1 Day 15 will be included in the analyses of the primary study endpoint.

A patient with tumor Ki67 value $> 2.7\%$ on Cycle 1 Day 15 of combination treatment is considered to not have had a complete cell cycle arrest.

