15.3 Trial Design

The expectation for complete cell cycle arrest, defined as $\leq 2.7\%$, at 2-4 weeks post neoadjuvant aromatase inhibitor alone, is 44% based on data from Z1031 Cohort B. Since PIK3CA mutation status does not affect neoadjuvant Ki67 response, the expected rate of complete cell cycle arrest for the PIK3CA mutant and wild type cohorts for single agent anastrozole is expected to be 44%.

The study is designed to ensure the sample size for the PIK3CA wild type cohort for the primary endpoint analysis. For the PIK3CA wild type cohort, thirty-three eligible patients will be enrolled. The sample size was chosen using Fleming's single-stage phase II design

to test the hypothesis that adding PD 0332991 would result in at least 50% improvement (44% versus 66%) in the complete cell cycle arrest rate, with 80% power and at 1-sided 0.05 significance level. If at least 20 patients in the cohort meet the criteria for complete cell cycle arrest, this regimen would be considered for future randomized trials.

Patients pre-registered to this trial and found to have PIK3CA mutation in the tumor are eligible to receive therapy in the PIK3CA mutant cohort. However, the enrollment to both cohorts will stop when 33 patients with PIK3CA wild type tumors have been enrolled and analyzed for the primary endpoint.

For the PIK3CA mutant cohort, depending on the frequency of mutation, 14 to 17 patients will be enrolled. The sample size for mutant cohort is determined primarily based on clinical feasibility rather than statistical power. However, according to the general guidelines regarding the sample size for translational studies[103], a sample size of 10-20 patients would provide reasonable precision for the estimation of pilot information regarding efficacy. If 10 complete cell-cycle arrest are observed out of 15 patients, for example, we will have 80% confidence that the “true” rate will fall between is ranged 47% and 83%.

For the endocrine resistant cohort, a Simon optimal two stage phase II clinical trial design will be used to assess whether the complete cell cycle arrest rate is at most 5% against the alternative that the complete cell cycle arrest rate is at least 20%. The study design proposed below yields a 90% chance of detecting a complete cell cycle arrest rate of at least 20% at an alpha level of 0.1.

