Stage 1: Enroll 12 patients. If at least one complete cell cycle arrest is documented among these 12 patients, continue to Stage 2. Otherwise terminate enrollment for this patient cohort and declare that this regimen has insufficient anti-tumor activity in the neoadjuvant setting to recommend it for further testing in this patient population.

Stage 2: Enroll an additional 25 patients. If at most 3 complete cell cycle arrests are documented among the 37 total patients enrolled, this regimen will be considered to have insufficient anti-tumor activity in the neoadjuvant setting to recommend it for further testing in this patient population. Otherwise, this regimen may be recommended for further testing in the neoadjuvant setting for this patient population. For such a design, we will only have 7% chance to erroneously stop the trial at the 1st-stage if the true the complete cell cycle arrest rate is at least 20%. Conversely, there will be 54% chance to stop the trial at the 1st-stage if the true the complete cell cycle arrest rate is 5% or less.

Adverse events, the pace of accrual, other scientific discoveries, or changes in standard of care will be taken into account in any decision to terminate this trial earlier than designed.

A 90% confidence interval for the true complete cell cycle arrest rate will be calculated using the Duffy-Santner approach.

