15.4 Sample Size and Trial Duration

We anticipate that 4-6 patients per month with clinical stage 2 or 3 estrogen receptor positive and HER2 negative invasive breast cancer will be screened for the *PIK3CA*. Approximately 40% of the patients have breast cancer with PIK3CA hotspot mutations. Thus, approximately 55 women with clinical stage 2 or 3 estrogen receptor positive and HER2 negative invasive breast cancer will be screened to enroll 33 evaluable patients to the PIK3CA wild type cohort.

The period encompassing enrollment, study treatment, and surgery will be about 20 months.

For the endocrine resistant cohort, we anticipate enrolling about one patient per month, completing Stage 1 in the approximately one year. If Stage 1 is successful, we will consider adding more sites to the study.

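### Sections 12.1 and 12.3 accept a later-cycle Ki67 for complete cell cycle arrest, sections 15.2 and 2.1 accept only C1D15, and nothing says which rule feeds the 12/37 counts in the endocrine-resistant cohort

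*Combined protocol and SAP*

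**What the plan says.** Two parts of the current text define who is scored for complete cell cycle arrest (Ki67 of 2.7% or less).

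- **Later cycle allowed.** Section 12.1: "In patients without C1D15 Ki67, Ki67 on D15 of subsequent cycles could be used instead". Section 12.3 makes this an analysis-set rule: women who "have tumor Ki67 determined on C1D15 (or a subsequent cycle) are included in the analysis of complete cell cycle arrest".
- **C1D15 only.** Section 15.2 says that women who begin the combination and "have an evaluable tumor Ki67 on Cycle 1 Day 15 will be included in the analyses of the primary study endpoint". Objective 2 in section 2.1 asks for the arrest rate "following 2 weeks (C1D15) of neoadjuvant PD 0332991 in combination with anastrozole in women with clinical stage II or III ER+/HER2- endocrine-resistant breast cancer".

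The case is foreseen. Note Q to the calendar in section 10.2 offers an optional biopsy on Day 15 of Cycle 2, 3 or 4 when the C1D15 biopsy was missed or its Ki67 was indeterminate. Note P lets the C1D15 biopsy itself run to C1D20.

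Section 15.3 sets the decision rule for the endocrine-resistant cohort. Stage 1: "If at least one complete cell cycle arrest is documented among these 12 patients, continue to Stage 2". Stage 2: "If at most 3 complete cell cycle arrests are documented among the 37 total patients enrolled", the regimen is judged insufficiently active. Neither sentence says which Ki67 value counts, or what happens to a woman who has none at C1D15. For the wild-type cohort the plan is clearer: section 15.3 says that "the enrollment to both cohorts will stop when 33 patients with PIK3CA wild type tumors have been enrolled and analyzed for the primary endpoint", and section 15.4 plans the number "screened to enroll 33 evaluable patients to the PIK3CA wild type cohort".

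**The concern.** The two rules can give different counts from the same women, and the cut-offs are small integers. The wording in 12.1 is permissive, so the plan does not settle which count decides.

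The values are also not alike. C1D15 falls 2 weeks after the combination starts. With 28-day cycles, Day 15 of Cycles 2, 3 and 4 falls 42, 70 and 98 days after C1D1, that is 6, 10 and 14 weeks. A substituted value therefore answers a different question from the 2-week objective. It can raise the number of arrests but never lower it.

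The trial is open label, and section 9.3.3 makes the C1D15 Ki67 available in real time. With no rule fixed, the choice between sections could be made after the Ki67 values are known. The endocrine-resistant cohort is the one neoadjuvant cohort still enrolling (section 3.0), so its decisions are the ones exposed.

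**Working it through.** **Inputs from the documents.** Stop at 0/12; insufficient at 3 or fewer of 37; null rate 5%, target rate 20%; stated power 90% and alpha 0.1; stated Stage 1 stopping 54% at 5% and 7% at 20% (section 15.3). In the closed cohorts 45 of 50 women were evaluable at C1D15 (section 1.8), so 5/50 = 10% were not (exact 95% CI 3.3% to 21.8%).

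**Assumptions.** A share m lacks C1D15. A share u of those women has a later Day 15 biopsy. The arrest rate p is the same on later biopsies. Women without C1D15 stay in the 12 or 37 as non-arrests and are not replaced.

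**1. The plan's own figures.** With X1 arrests among 12 and X2 among the next 25, P(success) = sum over x ≥ 1 of P(X1 = x) × P(X2 ≥ 4 − x).
- p = 0.20: power 90.2%; Stage 1 stop 0.80^12 = 6.9%.
- p = 0.05: false-positive rate 9.3%; Stage 1 stop 0.95^12 = 54.0%.

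The stated design reproduces.

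**2. How one value reverses a decision.**

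| Data | C1D15 only | Later value allowed |
|---|---|---|
| First 12: 0 arrests at C1D15, one later value ≤ 2.7% | 0/12, stop | 1/12, continue |
| All 37: 3 arrests at C1D15, one later value ≤ 2.7% | 3/37, insufficient | 4/37, further testing possible |

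The C1D15-only column needs the no-replacement assumption. Section 15.2 on its own would leave 0 of 11 evaluable in the first row, and section 15.3 has no rule for 11.

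**3. How often the final verdicts differ.** The effective arrest rate per enrolled woman is p(1 − m) under C1D15 only and p(1 − m + mu) with substitution. The second count is never below the first, so the share of trials with opposite verdicts is the difference in P(success). For m = 0.10:

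| True rate p | Rate, C1D15 only | P(success), C1D15 only | P(success), u = 100% | Difference, u = 0 to 100% |
|---|---|---|---|---|
| 20% | 0.180 | 85.7% | 90.2% | 0 to 4.5 points |
| 10% | 0.090 | 37.1% | 44.7% | 0 to 7.6 points |
| 5% | 0.045 | 6.9% | 9.3% | 0 to 2.4 points |

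At p = 20%, intermediate uptake gives 1.0 point (u = 20%, rate 0.184, 86.7%) and 2.5 points (u = 50%, rate 0.19, 88.2%).

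At Stage 1 with p = 20%, the wrong-stop probability is 0.82^12 = 9.2% under C1D15 only, against 0.81^12 = 8.0% at u = 50% and 0.80^12 = 6.9% at u = 100%.

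**4. A separate effect.** The fall from 90.2% to 85.7% under C1D15 only comes from missing biopsies without replacement. It would remain if 12.1 and 12.3 were deleted.

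**The case against.** The strongest reply is that the text has a natural order. Section 15.2 is headed as the primary endpoint and is the only place that names the set for the primary analysis. The objectives say C1D15, and section 1.8 reports the closed cohorts by evaluability at C1D15 for the primary endpoint. Section 12.1 only permits substitution, and 12.3 speaks of the arrest analysis without calling it primary. This is a fair reading and it points to the right fix. It remains an inference: no section states the order, and 12.3 defines an analysis set for the same endpoint.

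Mitigation also counts. C1D15 sampling is mandatory in this cohort, and a repeat biopsy is possible when the first is inadequate (sections 9.1.3 and 9.3.3), so missing values may be few.

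A reader might infer more than the documents support:

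- **That 15.2 by itself stops the cohort at Stage 1.** It contains no stopping rule. The stop follows only if the woman without C1D15 is kept among the 12 as a non-arrest.
- **That the conflict costs the design its power.** That loss is due to missing data without replacement.
- **That opposite verdicts are common.** A figure as high as 12.6% at a true rate of 20% needs 22% missing, about the upper confidence limit from other, closed cohorts, together with full uptake of an optional biopsy. The 5 unevaluable women have no stated cause, and section 1.9.7 makes some women inevaluable because of estradiol, so not all 5 need lack a C1D15 Ki67.
- **That alpha is broken.** With equal arrest rates on later biopsies, the false-positive rate is at most 9.3% under either rule.
- **That a rule was picked after seeing results.** Nothing in the documents shows this.

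**Conclusion.** The conflict is real and sits in current text. For the endocrine-resistant cohort, the plan does not say whether a later-cycle Day 15 Ki67 can supply the arrest that continues the cohort or carries it past the final cut-off. It should be resolved before either count is made.

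The consequence is possible rather than likely. A reversal needs a woman without C1D15, a later value of 2.7% or less, and a count at or near a cut-off. The ranges in the working put it between 0 and 7.6% of trials across true rates of 5%, 10% and 20%. They rest on 10% missing, no replacement and equal arrest rates on later biopsies. The 10% is borrowed from the closed cohorts, and both missingness and uptake in this cohort are unknown. The textual mismatch is certain; its practical size is not.

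The wild-type decision is not in play: section 1.8 reports 22 arrests, already above the cut-off of 20.

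**What to change.** 1. State that section 15.2 governs the primary endpoint and the 12 and 37 counts: Ki67 at C1D15, with the window to C1D20 in note P. This agrees with objective 2.1 and with how section 1.8 reported the closed cohorts.
2. Amend 12.1 and 12.3 so that later Day 15 values enter only a labelled sensitivity analysis of arrest.

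These two changes are wording only, with no new biopsy or visit. The downside is that a few women's later values leave the primary count. Adopting the later-cycle rule throughout would also remove the conflict, but it would mix 2 weeks of combination therapy with 6 to 14 weeks.

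3. Separately, say in section 15.3 whether the 12 and 37 are women with an evaluable C1D15 Ki67. If unevaluable women count as non-arrests and are not replaced, restate the power: about 85.7% at 10% missing, against the stated 90%. Replacement would keep the planned 90.2% but is optional, because it costs enrolment. At 10% missing, 37/0.90 = 41.1, so about 4 more women, or about 4 months at the planned one per month. At 22% missing, 37/0.78 = 47.4, so about 10 more women and 10 months unless sites are added.

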12.2 Treatment Resistance

A patient is said to have resistance disease if her Ki67 is $> 10\%$ on biopsy taken on Cycle 1 Day 15 or if progressive disease is documented any time during neoadjuvant endocrine therapy.

12.3 Surgery

A pathologic complete response (pCR) is defined as no histology evidence of invasive tumor cells in the surgical breast specimen and sentinel or axillary lymph nodes.

All eligible women who have been begun treatment with combination therapy and have tumor Ki67 determined on C1D15 (or a subsequent cycle) are included in the analysis of complete cell cycle arrest. Women with tumor Ki67>2.7% on therapy are considered to have a non-complete cell cycle arrest.

12.4 Post-surgery

Local recurrence is defined as histologic evidence of ductal carcinoma in situ or invasive breast cancer in the ipsilateral breast or chest wall.

Regional recurrence is defined as the cytologic or histologic evidence of disease in the ipsilateral internal mammary, ipsilateral supraclavicular, ipsilateral infraclavicular and/or ipsilateral axillary nodes or soft tissue of the ipsilateral axilla.

Distant recurrence is defined as the cytologic, histologic, and/or radiographic evidence of disease in the skin, subcutaneous tissue, lymph nodes (other than local or regional metastasis), lung, bone marrow, central nervous system or histologic and/or radiographic evidence of skeletal or liver metastasis.

Second primary breast cancer is defined histologic evidence of ductal carcinoma in situ or invasive breast cancer in the contralateral breast or chest wall.

Second primary cancer (non-breast) is defined as any non-breast second primary cancer other than squamous or basal cell carcinoma of the skin, melanoma in situ, or carcinoma in situ of the cervix is to be reported and should be confirmed histologically whenever possible.

13.0 DATA AND SAFETY MONITORING

In compliance with the Washington University Institutional Data and Safety Monitoring Plan, the Data and Safety Monitoring Committee (DSMC) will meet to review toxicity data at least every 6 months following the activation of the first secondary site. The report will be prepared by the statistician with assistance from the study team and will be submitted to the Quality Assurance and Safety Monitoring Committee (QASMC). This report will include:

- HRPO protocol number, protocol title, Principal Investigator name, data coordinator name, regulatory coordinator name, and statistician
- Date of initial HRPO approval, date of most recent consent HRPO approval/revision, date of HRPO expiration, date of most recent QA audit, study status, and phase of study

- History of study including summary of substantive amendments; summary of accrual suspensions including start/stop dates and reason; and summary of protocol exceptions, error, or breach of confidentiality including start/stop dates and reason
- Study-wide target accrual and study-wide actual accrual including numbers from participating sites
- Protocol activation date at each participating site
- Average rate of accrual observed in year 1, year 2, and subsequent years at each participating site
- Expected accrual end date and accrual by site.
- Objectives of protocol with supporting data and list the number of participants who have met each objective
- Measures of efficacy
- Early stopping rules with supporting data and list the number of participants who have met the early stopping rules
- Summary of toxicities at all participating sites
- Abstract submissions/publications
- Summary of any recent literature that may affect the safety or ethics of the study

Until such a time as the first secondary site activates this protocol, a semi-annual DSM report to be prepared by the study team will be submitted to the QASM Committee beginning 6 months after study activation at Washington University.

The study principal investigator and Research Patient Coordinator will monitor for serious toxicities on an ongoing basis. Once the principal investigator or Research Patient Coordinator becomes aware of an adverse event, the AE will be reported to the HRPO and QASMC according to institutional guidelines.

A DSMC will consist of no fewer than 3 members including 2 clinical investigators and a biostatistician. Like investigators, DSMC members are subject to the Washington University School of Medicine policies regarding standards of conduct. Individuals invited to serve on the DSMC will disclose any potential conflicts of interest to the trial principal investigator and/or appropriate university officials, in accordance with institution policies. Potential conflicts that develop during a trial or a member's tenure on a DSMC must also be disclosed.

Refer to the Washington University Quality Assurance and Data Safety Monitoring Committee Policies and Procedures for full details on the responsibilities of the DSMC at http://www.siteman.wustl.edu/uploadedFiles/Research_Programs/Clinical_Research_Resources/Protocol_Review_and_Monitoring_Committee/QASMCQualityAssurance.pdf

14.0 AUDITING

Since Washington University is the coordinating center, each site will be audited annually by Siteman Cancer Center personnel (QASMC) unless the outside institution has an auditing mechanism in place and can provide a report. The outside sites will be asked to send copies of all audit materials, including source documentation. The audit notification will be sent to the

Washington University Research Patient Coordinator, who will obtain the audit materials from the participating institution.

Notification of an upcoming audit will be sent to the research team one month ahead of the audit. Once accrual numbers are confirmed, and approximately 30 days prior to the audit, a list of the cases selected for review (up to 10 for each site) will be sent to the research team. However, if during the audit the need arises to review cases not initially selected, the research team will be asked to provide the additional charts within two working days.

Additional details regarding the auditing policies and procedures can be found at <https://siteman.wustl.edu/wp-content/uploads/2015/10/QASMC-Policies-and-Procedures-03.31.2015.pdf>

15.0 STATISTICAL CONSIDERATIONS

15.1 Purpose

This is an open label phase II trial consisting of three independent cohorts that are run separately—the PIK3CA wild type cohort, the PIK3CA mutant cohort, and the endocrine resistant cohort—in women with clinical stage 2 or 3 estrogen receptor positive and HER2 negative invasive breast cancer to assess the anti-tumor activity (in terms of rate of complete cell cycle arrest) and safety profile of neoadjuvant PD 0332991 in combination with anastrozole for postmenopausal women or with anastrozole and goserelin for premenopausal women.

